1.2 Purpose

The purpose of this randomized, actively controlled, double-blind study with prospective data collection is to assess differences between sacubitril/valsartan versus enalapril in distance walked in a 6 minute walk test (6MWT) and increasing non-sedentary daytime physical activity in HFrEF patients. To this end, the 6MWT will be performed before the patients are randomized to any of the treatments and at 12 weeks of randomized treatment whereas physical activity will be continuously measured by means of a wrist-worn accelerometry device from 2 weeks before until 12 weeks after start of study therapy (sacubitril/valsartan or enalapril).

2 Study objectives and endpoints

The main aim of the study is to elucidate any potential change in the 6MWT as assessed in the distance walked before treatment randomization compared to the end of study in both sacubitril/valsartan and enalapril treated patients and to assess differences between sacubitril/valsartan versus enalapril in improving non-sedentary daytime physical activity in HFrEF patients. The study objectives and the related endpoints are presented in [Table 2-1](#). Patients will be performing the 6MWT at visit 2, 4, 5 and 6 and will be wearing wrist-worn accelerometry devices over the time period between two weeks prior to (baseline) and 12

weeks after randomization to receive either sacubitril/valsartan or enalapril. For each patient, an individual baseline activity level will be recorded over the two weeks prior to randomization.

Table 2-1 Objectives and related endpoints

[figure not shown]
Objective	Endpoint	Analysis
Primary		
To assess changes from baseline (week 0) in exercise capacity assessed by means of the 6-minute walking test at week 12	
Title: Change from baseline in 6-minute walking test
 
Units of measure: descriptive statistics for quantitative data, absolute and relative frequency distributions including 95% confidence intervals.
 
Time frame: baseline (week 0, at randomization) and week 12
	Section 9.4
To assess changes in daily non-sedentary daytime activity between baseline and after 12 weeks of treatment in sacubitril/valsartan vs. enalapril treated patients.	
Title: Change in mean daily non-sedentary daytime activity between baseline¹ and end of study.
 
Description: non-sedentary physical activity is defined as ≥ 178.50 activity counts per minute; the average number of minutes per day spent in non-sedentary physical activity will be calculated over 14 days before randomization (baseline¹) and the last 14 days of treatment (i.e. week 10 to week 12).
 
Units of measure: descriptive statistics for quantitative data, absolute and relative frequency distributions including 95% confidence intervals.
 
Time frame: baseline¹ epoch (i.e. week -2 to week 0), end of study² epoch (i.e. week 10 to week 12)
	Section 9.4
Secondary		
To assess changes from baseline (week 0) in exercise capacity assessed by means of the 6-minute walking test at week 12	
Title: Proportion of patients with improved performance ($\geq 30m$) (Tager et al., 2014, Shoemaker et al., 2013) in the 6-minute walking test.
 
Units of measure: descriptive statistics for quantitative data, absolute and relative frequency distributions including 95% confidence intervals.
 
Time frame: baseline (week 0, at randomization) and week 12
	Section 9.5
To demonstrate that sacubitril/valsartan is superior in improving exercise capacity as assessed by the six-minute walk test (6MWT) at week 12 in a subset of patients with baseline six-minute walk distance	
Title: Proportion of patients with improved performance ($\geq 30m$) (Shoemaker et al., 2013, Tager et al., 2014) in the 6-minute walking test and which walked equal to or less than 300
	Section 9.5

[figure not shown]
Objective	Endpoint	Analysis
equal to or less than 300 meters	meters at baseline Units of measure: descriptive statistics for quantitative data, absolute and relative frequency distributions including 95% confidence intervals. Time frame: baseline (week 0, at randomization) and week 12	Section 9.5
To demonstrate that sacubitril/valsartan is superior in improving exercise capacity as assessed by the six-minute walk test (6MWT) at week 12 in the patients with baseline six-minute walk distance between 100-450 meters.	Title: Proportion of patients with improved performance ($\geq 30m$) (Shoemaker et al., 2013 , Tager et al., 2014) in the 6-minute walking test and which walked 100-450 meters at baseline Units of measure: descriptive statistics for quantitative data, absolute and relative frequency distributions including 95% confidence intervals. Time frame: baseline (week 0, at randomization) and week 12	Section 9.5
To assess changes from baseline (week 0) in exercise capacity assessed by means of the 6-minute walking test at weeks 4, 8 and 12	Title: Change from baseline in 6-minute walking test Units of measure: descriptive statistics for quantitative data, absolute and relative frequency distributions including 95% confidence intervals. Time frame: baseline (week 0, at randomization), under treatment (week 4, week 8, week 12)	Section 9.5
To assess changes in daily non-sedentary daytime activity between baseline and after 12 weeks of treatment in sacubitril/valsartan vs. enalapril treated patients.	Title: Proportion of patients who show increased levels ($\geq 10\%$ increase) of non-sedentary daytime physical activity at week 12 compared to baseline Description: non-sedentary physical activity is defined as ≥ 178.50 activity counts per minute; the average number of minutes per day spent in non-sedentary physical activity will be calculated over 14 days before randomization (baseline ¹) and the last 14 days of treatment (i.e. week 10 to week 12). Units of measure: descriptive statistics for quantitative data, absolute and relative frequency distributions including 95% confidence intervals. Time frame: baseline ¹ epoch (i.e. week -2 to week 0), end of study ² epoch (i.e. week 10 to week 12)	Section 9.5

Objective	Endpoint	Analysis
To compare the effects of sacubitril/valsartan vs. enalapril on patients' symptom progression by means of the Patient Global Assessment (PGA) questionnaire at week 4, week 8 and week 12.	
Title: PGA score at week 4, week 8 and week 12.
 
Title: Proportion of patients with improved symptoms of HF as assessed by PGA.
 
Description: PGA score of symptoms of HF will be assessed as previously described.
 
Units of measure: descriptive statistics for quantitative data, absolute and relative frequency distributions including 95% confidence intervals.
 
Time frame: week 4, week 8, week 12
	Section 9.5
To assess dynamics of changes from baseline ¹ in daily non-sedentary daytime physical activity in sacubitril/valsartan vs. enalapril treated patients in weekly and two-weekly intervals.	
Title: Change from baseline¹ in mean daily non-sedentary daytime activity in weekly and two-weekly intervals
 
Title: Proportion of patients at weekly and two-weekly intervals who show increased levels ($\geq 10\%$ increase) of mean daily non-sedentary daytime physical activity compared to baseline
 
Description: mean daily non-sedentary daytime physical activity (definition see above) will be calculated over weekly and two-weekly epochs and compared to baseline (¹ for two-weekly intervals). For comparison of weekly intervals, the last 7 days of baseline recording prior to randomization will serve as baseline. While two-weekly intervals allow for more stable baseline and post-titration values, weekly intervals will be used to visualize and analyze the dynamics of change post randomization.
 
Units of measure: descriptive statistics for quantitative data, absolute and relative frequency distributions including 95% confidence intervals.
 
Time frame: baseline¹ epoch (i.e. week -2 to week 0 for two-weekly intervals or last 7 days prior to randomization for comparison of weekly intervals), weekly or two-weekly from week 0 to week 12.
	Section 9.5
To assess changes from baseline ¹ in mean daily non-sedentary daytime physical activity classified by its intensity for sacubitril/valsartan vs. enalapril treated patients after week 4, week 8 and week 12.	
Title: Change from baseline¹ in mean daily light and moderate-to-vigorous non-sedentary daytime physical activity between baseline¹ and different time points under treatment.
 
Description: non-sedentary physical
	Section 9.5

Objective	Endpoint	Analysis
To assess the difference in non-sedentary daytime physical activity between sacubitril/valsartan vs. enalapril treated patients during the treatment period (weeks 0 to 12).	
activity is defined as ≥ 178.5 activity counts per minute; light physical activity is defined as $178.5 - 565.5$ counts per minute; moderate-to-vigorous activity is defined as > 565.5 counts per minute. The average number of minutes per day spent in the different non-sedentary physical activity categories (light and moderate-to-vigorous) will be calculated over 14 day epochs.
 
Units of measure: descriptive statistics for quantitative data.
 
Time frame: baseline¹ epoch (i.e. week -2 to week 0), week 2 to week 4, week 6 to week 8, week 10 to week 12.
	
Title: Total weekly time spent in non-sedentary daytime physical activity.
 
Title: Total weekly time spent in light non-sedentary daytime physical activity.
 
Title: Total weekly time spent in moderate-to-vigorous non-sedentary daytime physical activity
 
Description: Non-sedentary physical activity is defined as ≥ 178.5 activity counts per minute; light physical activity is defined as $178.5 - 565.5$ counts per minute; moderate-to-vigorous activity is defined as > 565.5 counts per minute. The total time spent in non-sedentary physical activity and the time spent in light and moderate-to-vigorous physical activity will be calculated for each patient in weekly intervals and the temporal course for each patient will be assessed.
 
Units of measure: descriptive statistics for quantitative data.
 
Time frame: week 0 to week 12 in weekly epochs

To assess changes from baseline ¹ on M6min (an actigraphy-based measure of the peak six minutes of daytime physical activity) in sacubitril/valsartan vs. enalapril treated patients after week 4; week 8 and week 12.	
Title: Change from baseline¹ in M6min.
 
Title: Proportion of patients with increased M6min compared to baseline¹ at week 4, week 8 and week 12.
 
Description: M6min is a parameter derived by validated algorithms of the software that will be used to pre-process actigraphy data. The
	
Section 9.5

Objective	Endpoint	Analysis
	
parameter reflects the peak 6 minutes of physical activity. The mean daily M6min will be calculated over 14 day epochs.
 
Units of measure: descriptive statistics for quantitative data, absolute and relative frequency distributions including 95% confidence intervals.
 
Time frame: baseline¹ epoch (i.e. week -2 to week 0), week 2 to week 4, week 6 to week 8, week 10 to week12
	

¹ For all objectives/endpoints assessed by means of actigraphy, the baseline value is obtained over a period of two weeks prior to randomization, i.e. weeks -2 to week 0.

3 Investigational plan

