6.3.2 Summary Statistics

In general, categorical data will be summarized with number of missing values, frequencies and percentages, while continuous data will be reported using number of patients, number of missing values, mean, standard deviation (SD), median, Q1, Q3, minimum and maximum. Minimum and maximum values will be provided with the same level of accuracy as raw data; means and medians will be provided with an additional decimal place and SD with 2 additional decimal places.

For secondary objectives and continuous variables, the 95% CI will be added to the statistics.

Comparing continuous variables between groups, if the variable has a normally distributed data a two sample (independent group) t-test will be used, but if the variable has a non-Normally distributed data then the non-parametric Mann–Whitney–Wilcoxon (Wilcoxon rank sum) test will be applied.

Comparing proportions of a categorical outcome between groups of treatment: usually chi-square test will be used, but when more than 20% of cells have expected frequencies < 5 the Fisher's exact test will be applied.

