6.3.6 Secondary Efficacy Analyses

Proportion of patients with improved performance (≥ 30 m) in 6-minute walking test at week 12 compared to baseline. The comparison of patient groups will be carried out using logistic regression model with factors treatment and baseline NYHA class (NYHA II vs. III/IV) and the baseline value as further covariate. The Odds Ratio for the factor treatment and its 95%-confidence interval will be given.

Proportion of patients with improved performance (≥ 30 m) in 6-minute walking test at week 12 compared to baseline in a subset of patients with baseline 6-minute walk distance equal to or less than 300 meters. The comparison of patient groups will be carried out using logistic regression model with factors treatment and baseline NYHA class (NYHA II vs. III/IV) and the baseline value as further covariate. The Odds Ratio for the factor treatment and its 95%-confidence interval will be given.

Proportion of patients with improved performance (≥ 30 m) in 6-minute walking test at week 12 compared to baseline in a subset of patients with baseline 6-minute walk distance between 100-450 meters. The comparison of patient groups will be carried out using logistic regression model with factors treatment and baseline NYHA class (NYHA II vs. III/IV) and the baseline value as further covariate. The Odds Ratio for the factor treatment and its 95%-confidence interval will be given.

Score of 6-minute walking test will be summarised at baseline, week 4, week 8 and week 12. Change from baseline values will be presented. The comparison of patient groups at week 12 compared to baseline will be analyzed using a two sample (independent group) t-test or a non-parametric Mann–Whitney–Wilcoxon (Wilcoxon rank sum) test, where applicable.

Proportion of patients who show increased levels ($\geq 10\%$ increase) of non-sedentary daytime physical activity at week 12 compared to baseline. The comparison of patient groups will be carried out using logistic regression model with factors treatment and baseline NYHA class (NYHA II vs. III/IV) and the baseline value as further covariate. The Odds Ratio for the factor treatment and its 95%-confidence interval will be given.

PGA scores will be tabulated at week 4, week 8 and week 12. The comparison of patient groups at week 4, week 8 and week 12 will be analyzed using a chi-square test or Fisher's exact test, where applicable.

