Proportion of patients with improved symptoms of HF as assessed by PGA, number and proportion will be tabulated at week 4, week 8 and week 12. The comparison of patient groups will be presented and analyzed using a chi-square test or Fisher's exact test, where applicable.

Change from baseline in mean daily non-sedentary daytime activity in weekly and two-weekly intervals will be summarised. The comparison of patient groups will be analyzed using a two sample (independent group) t-test or a non-parametric Mann–Whitney–Wilcoxon (Wilcoxon rank sum) test, where applicable.

Proportion of patients at weekly and two-weekly intervals who show increased levels ($\geq 10\%$ increase) of mean daily non-sedentary daytime physical activity compared to baseline will be tabulated. The comparison of patient groups will be presented and analyzed using a chi-square test or Fisher's exact test, where applicable.

Change from baseline in mean daily light and moderate-to-vigorous non-sedentary daytime physical activity between baseline and different time points under treatment (weekly or two-weekly from week 0 to week 12) will be summarised. The comparison of patient groups will be analyzed using a two sample (independent group) t-test or a non-parametric Mann–Whitney–Wilcoxon (Wilcoxon rank sum) test, where applicable.

Total weekly time spent in non-sedentary daytime physical activity will be summarised by week, from week 0 to week 12. The comparison of patient groups will be analyzed using a two sample (independent group) t-test or a non-parametric Mann–Whitney–Wilcoxon (Wilcoxon rank sum) test, where applicable.

[figure not shown]
Total weekly time spent in light non-sedentary daytime physical activity will be summarised by week, from week 0 to week 12. The comparison of patient groups will be analyzed using a

[figure not shown]
two sample (independent group) t-test or a non-parametric Mann–Whitney–Wilcoxon (Wilcoxon rank sum) test, where applicable.

Total weekly time spent in moderate-to-vigorous non-sedentary daytime physical activity will be summarised by week, from week 0 to week 12. The comparison of patient groups will be analyzed using a two sample (independent group) t-test or a non-parametric Mann–Whitney–Wilcoxon (Wilcoxon rank sum) test, where applicable.

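### Three responder families get only tabulated proportions and an unadjusted test, with no between-arm estimate specified, and the weeks 10-12 activity responder is tested by two methods.

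*Protocol*

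**What the plan says.** **Units of measure.** Protocol Table 2-1 gives the PGA, interval-activity and M6min endpoints the same unit: "absolute and relative frequency distributions including 95% confidence intervals". The responder endpoints concerned are improved symptoms on the PGA, the activity responder ("Proportion of patients at weekly and two-weekly intervals who show increased levels" of at least 10%), and "Proportion of patients with increased M6min compared to baseline" at weeks 4, 8 and 12.

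**General rules.** Under SAP 6.3.2, "categorical data will be summarized with number of missing values, frequencies and percentages". The same section adds: "For secondary objectives and continuous variables, the 95% CI will be added to the statistics".

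**Endpoint methods in SAP 6.3.6.**
- For the three 6MWT responders and the week-12 activity responder: "The comparison of patient groups will be carried out using logistic regression model with factors treatment and baseline NYHA class", with the baseline value as a further covariate and an odds ratio with 95% CI.
- For improvement on the PGA: "number and proportion will be tabulated at week 4, week 8 and week 12", followed by a chi-square or Fisher test.
- For the weekly and two-weekly activity responders and for increased M6min, the results are tabulated, and "The comparison of patient groups will be presented and analyzed using a chi-square test" or Fisher's exact test.

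**Status.** Protocol 9.5.1 prescribes logistic regression for the end-of-study activity responder only, leaves the other secondary test methods to the SAP, and makes all secondary tests exploratory without multiplicity control. Protocol 5.3 stratifies randomisation by NYHA class (II against III/IV).

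**The concern.** The SAP handles the same type of endpoint in two ways and gives no reason. Where the logistic model is used, the reader gets a between-arm effect and its precision. In the other three families the SAP asks for proportions by arm and a p-value. For exploratory endpoints with no multiplicity control, the estimate and its interval carry the information. A non-significant p-value does not separate no effect from an imprecise result.

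Whether a patient counts as a responder on change also depends strongly on the baseline value, because high baselines tend to fall and low ones to rise. Leaving out a baseline that is already collected loses power.

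The last two-weekly epoch repeats an endpoint that already has its own analysis. Two p-values by different methods then exist for one end-of-study quantity, and they can fall on opposite sides of 5%.

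**Working it through.** **1. The plan's own figure.** The documents give no power or sample size for any responder endpoint. The inputs used below come from the activity calculation in Protocol 9.8: two-sided 5%, 90% power, difference 20 min/day, SD of change 70. By the normal approximation, n = 2 × (1.960 + 1.282)² × 70² / 20² = 257.4, so 258 per arm. The t-test solution is 259, as stated.

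**2. Methods side by side (SAP 6.3.6 and Appendix 1).**

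| Responder endpoint | Between-arm method | Covariates | Effect with CI specified |
|---|---|---|---|
| 6MWT gain ≥30 m (all; baseline ≤300 m; baseline 100-450 m) | logistic | NYHA, baseline | odds ratio, 95% CI |
| Activity ≥10%, week 12 (Table 14.2-13) | logistic | NYHA, baseline | odds ratio, 95% CI |
| PGA improved, weeks 4, 8, 12 (Table 14.2-15) | chi-square/Fisher | none | none |
| Activity ≥10%, by interval (Table 14.2-17) | chi-square/Fisher | none | none |
| M6min increased, weeks 4, 8, 12 (Table 14.2-23) | chi-square/Fisher | none | none |

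The last three rows hold 3 + (12 weekly + 6 two-weekly) + 3 = 24 comparisons. One of them, weeks 10-12, has an adjusted odds ratio elsewhere. That leaves 24 − 1 = 23 with no between-arm estimate specified.

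**3. The duplicate.** In Table 2-1 the week-12 responder compares weeks 10-12 with the 14-day baseline, using a 10% threshold. The sixth two-weekly interval has the same window, baseline and threshold. Both SAP tables use the FAS. Neither is named as the result to report.

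**4. Cost of leaving out the covariates (simulation of the ≥10% activity responder).** From the plan: SD 70, correlation 0.5, effect 20 min/day, 300 per arm. Assumed: baseline mean 215 min/day (the plan gives 200-230), a correlation of 0.7 as the alternative, effects of 15 and 10 min/day as alternatives, and all 300 per arm analysable. A patient responds if follow-up ≥ 1.10 × baseline. Each setting has 1,500 trials and compares an uncorrected chi-square test with a logistic model.

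Set-up A has no NYHA effect and a logistic model with treatment and baseline. Set-up B assumes a NYHA difference of 30 min/day and a drift of −5 min/day, and the logistic model adds NYHA.

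| Set-up | Effect | Correlation | Chi-square | Logistic | Gain | Tests disagree at 5% |
|---|---|---|---|---|---|---|
| A | 20 | 0.5 | 75% | 84% | 9 | not recorded |
| A | 15 | 0.5 | 51% | 60% | 9 | not recorded |
| A | 20 | 0.7 | 92% | 95% | 3 | not recorded |
| B | 20 | 0.5 | 76.3% | 84.1% | 7.8 | 10.5% |
| B | 20 | 0.7 | 91.8% | 95.4% | 3.6 | 5.7% |
| B | 10 | 0.5 | 26.3% | 31.4% | 5.1 | 14.5% |
| B | 10 | 0.7 | 37.1% | 41.5% | 4.4 | 13.9% |
| B | 0 | 0.5 | 5.3% | 4.6% | – | 3.5% |
| B | 0 | 0.7 | 4.7% | 4.1% | – | 2.7% |

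The Monte Carlo standard error of a single power near 76% is √(0.76 × 0.24 / 1500), or about 1.1 points. With no effect, both tests hold their level within that kind of error. In set-up A at 20 min/day and correlation 0.5, the response rates are about 39% against 49%.

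**5. What an interval would show.** For an assumed 40% against 50% with 300 per arm, the half-width is 1.96 × √(0.4 × 0.6/300 + 0.5 × 0.5/300) = 0.079. The difference of 10 points would run from about 2 to 18 points.

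**The case against.** The strongest reply is that the SAP complies with the protocol. Protocol 9.5.1 asks for logistic regression on one responder endpoint and leaves the other tests to the SAP. In a randomised comparison the unadjusted chi-square test is valid, and no responder endpoint has a power target. All of that stands, so the choice is not an error. It is an unexplained inconsistency with a modest cost.

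Several stronger readings are tempting, and the documents do not support them:
- *These endpoints get nothing but a p-value.* Counts and percentages by arm are tabulated, and a reader could derive a crude difference and its interval from them.
- *The SAP plans no intervals for them.* The CI sentence in SAP 6.3.2 can be read as covering all secondary objectives, or only continuous secondary variables. The wording is ambiguous, and on neither reading does it name a between-arm effect.
- *Table 2-1 requires a between-arm effect.* It attaches CIs to frequency distributions. An odds-ratio CI does not meet that unit either, so the question of CIs for proportions also touches the four logistic endpoints.
- *All three families should be baseline-adjusted.* The PGA is first completed at Visit 4 and rates change from the pre-intervention condition, so it has no baseline. The power figures apply to the activity responder and were not derived for PGA or M6min.

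The interval table does serve a separate objective, the dynamics of change. Protocol 9.5.1 also asks for the end-of-study responder with and without imputation, while nothing comparable is specified for the interval series. That explains why two tables exist. It does not say which weeks 10-12 result stands, and it means that even the counts could differ.

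**Conclusion.** The point holds in limited form. Three responder families lack a specified between-arm estimate and interval, while four others have an adjusted odds ratio with CI. Whether the proportions themselves carry CIs is ambiguous. The weeks 10-12 activity responder is tested twice with no stated precedence.

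For the activity responder, the unadjusted test gives up roughly 3 to 9 points of power over the range examined (baseline mean 215 min/day assumed, SD 70, effect 15-20 min/day, correlation 0.5-0.7, 300 per arm). At 20 min/day the two weeks 10-12 tests disagree in about 11% of trials at correlation 0.5 and about 6% at 0.7.

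A reader might infer that the chi-square results would be biased or that a trial conclusion is at risk. Neither follows: the tests keep their level, the endpoints are exploratory, and no primary analysis or sample size is affected.

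**What to change.** - **SAP 6.3.6 and Tables 14.2-15, 14.2-17 and 14.2-23:** reuse the logistic model already planned, with treatment and NYHA stratum. Add the matching baseline for activity (the last 7 days before randomisation for weekly intervals, 14 days for two-weekly) and for M6min. Use NYHA only for the PGA. Report the odds ratio with its 95% CI beside the proportions by arm.
- **SAP 6.3.2:** state that secondary responder proportions carry 95% CIs, which settles the Table 2-1 unit for every responder endpoint.
- **Weeks 10-12:** name Table 14.2-13 as the single test. Table 14.2-17 shows the proportions for that interval and refers to it.

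The cost is a few sentences of SAP text and reuse of an existing program. Nothing changes in data collection or conduct. The downside is that sparse cells will need a pre-stated fallback to an exact or unadjusted interval. The adjusted odds ratio will also differ somewhat from the crude one implied by the tabulated proportions, which a table footnote can explain.
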